6.3.1.2. TEAE Status When Start Date Is Unknown

The following rules will apply in cases where start date of an AE is unknown:

- If the AE onset date is unknown and the end date is after the date of CCH injection on Day 1 or ongoing, then the AE will be considered a TEAE.
- If the AE onset date is unknown and the end date is before the date of CCH injection on Day 1, then the AE will not be considered a TEAE.
- If both the start date and end date are unknown (or ongoing), then the AE will be considered a TEAE, following the worst-case principle.

6.3.1.3. Missing EFP Onset Date

Missing EFP onset day will be imputed as the first day of the month and missing onset month will be imputed as January. If the EFP onset date is indicated as completely unknown but starting less than 5 years ago, the EFP onset date will be imputed as the informed consent date minus 5 years. If the EFP onset date is indicated as completely unknown but starting more than 5 years ago, the EFP onset date will not be imputed. Missing EFP medication/treatment end days will be imputed with the last day of the month and missing end months will be imputed with December, except if the end year is equal to the date of injection year and then the EFP medication/treatment end date will be imputed with the first injection date.

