3.11. Prohibited Medications and Therapies

The following medications are prohibited for subjects during the study:

- Anticoagulants (warfarin, heparin, direct thrombin inhibitors, Factor X inhibitors) and antiplatelet agents (aspirin >150 mg/day and P2Y12 inhibitors, such as clopidogrel),

which can cause additional bruising. However, the use of aspirin at a dose level of ≤ 150 mg per day will be permitted during study.

The following procedures/treatments are not allowed in the selected treatment region (both buttocks or both thighs) during the course of the study (from the Screening Visit through the Day 265 Visit):

- Liposuction.
- Any injectable treatment (eg, KYBELLA) or any similar treatment that could destroy fat cells and/or remove fat deposits.
- Injections (eg, mesotherapy); radiofrequency device treatments; laser treatment; buttock implant treatment; cryolipolysis; or surgery (including subcision and/or powered subcision).
- Any investigational treatment for EFP (other than CCH as prescribed in this study).
- Endermologie or similar treatments.
- Massage therapy.
- Creams (eg, Celluvera, TriLastin) and/or home therapies to prevent or mitigate EFP.

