4.3. Prior/Concomitant Medications and Procedures

All medications will be coded using the World Health Organization (WHO) Drug Dictionary by active ingredient and anatomical therapeutic chemical (ATC) classification of ingredients. The dictionary version used is defined in the Data Management Plan.

Any medications/procedures within 90 days prior to the Screening Visit will be classified as prior medications/procedures.

Any medications/procedures from the Screening Visit through the Day 265 Visit will be classified as concomitant medications/procedures.

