4.4. Prior EFP Treatment

Prior EFP treatment will be obtained from the prior/concomitant medication and/or prior/concomitant procedure pages of the eCRF. If on either of these pages a medication or procedure is reported with the indication ‘EFP/Cellulite’ and the start date is prior to the Screening Visit, then the medication or procedure will be considered a prior EFP treatment.

All medications will be classified as EFP Drug. All procedures will be classified into one of the following groups:

- Liposuction.
- Laser.
- Massage.
- Radiofrequency.
- Mesotherapy.
- Cream.

- Other.

The classification will be reviewed and approved by the study medical monitor. Any EFP treatment used after the Day 1 visit will be noted and reported as a protocol violation.

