6.2. Derived Variables

Refer to Table 12 below for derived variables and their definitions for various study parameters.

Table 12: Derived Variables and Definition

Variable	Definition
Height (cm)	If height is recorded in inches, then height is equal to the recorded value multiplied by 2.54 and then rounded to 1 decimal place.
Weight (kg)	If weight is recorded in pounds, then weight is equal to the recorded value multiplied by 0.454 and then rounded to 1 decimal place.
Baseline	Baseline is defined as the last non-missing measurement/assessment prior to the CCH injections given at Day 1. Any assessments performed at an unscheduled visit will be considered in the calculation of baseline, if the unscheduled assessment is the closest value preceding the study drug injection.
Study Day	Study Day will be computed as Date of Assessment – Date of Day 1 + 1 for assessments on or after Day 1, else study day will be computed as Date of Assessment – Date of Day 1.
Change from Baseline	Change from baseline will be derived as post-baseline visit/time point value – the baseline value.
Last Date in the Study	Last date in study is defined as: 
 • The date of Day 265 (Biopsy follow-up visit) if the subject completes the study • The date of early termination visit if the subject is terminated early from study at a non-scheduled visit • The date of the latest scheduled visit if the subject is terminated early from study at a scheduled visit or lost to follow-up.
Age (Years) at EFP Symptom Onset	Date of EFP symptoms reported – Date of Birth/365.25. See Section 6.3.1.3 for handling of partial or unknown EFP symptom onset dates.
Time (Years) Since Last EFP Treatment	Date of most recent EFP treatment – Date of informed consent/365.25. See Section 6.3.1.3 for handling of partial or unknown EFP treatment dates.
Duration (Minutes) of Exposure at Each Visit	Date/Time of Last Injection – Date/Time of First Injection
Duration of AE(Days)	AE end date – AE start date + 1
AE Onset Day	AE start date – Date of Day 1 + 1.

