6.3.1. Imputation of Partial Dates

The following rules will apply in cases of partial dates in concomitant medications and procedures:

- If the start date is partial with month and year present, then missing day will be imputed with the first day of the month. Whereas if the end date is partial with month and year present then missing day will be imputed with the last day of the month.
- If only year is present in the start date, then missing day and month will be imputed with first day of January. Whereas if only year is present then missing day and month will be imputed with the last day of December.

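### SAP 6.3.1.3, read literally, overwrites a known earlier stop month of a cellulite treatment with the first injection date, and Table 12 subtracts in the wrong order when it uses that date

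*SAP*

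**What the plan says.** Two SAP rules bear on a partial end date of a cellulite treatment.

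- **SAP 6.3.1**, for concomitant medications and procedures: "if the end date is partial with month and year present then missing day will be imputed with the last day of the month". It has no exception for the year.
- **SAP 6.3.1.3**, for EFP treatments, starts the same way: "Missing EFP medication/treatment end days will be imputed with the last day of the month and missing end months will be imputed with December". It then adds: "except if the end year is equal to the date of injection year and then the EFP medication/treatment end date will be imputed". The value assigned is Day 1: "the EFP medication/treatment end date will be imputed with the first injection date".

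EFP treatments are taken from the same prior/concomitant medication and procedure pages (SAP 4.4), and the SAP does not say which rule takes precedence.

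Three other provisions use or frame the date:

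- **SAP 4.3**: "Any medications/procedures from the Screening Visit through the Day 265 Visit will be classified as concomitant medications/procedures".
- **SAP 4.4** sets prior status by the start date: if "the start date is prior to the Screening Visit, then the medication or procedure will be considered a prior EFP treatment". It reports a violation only for EFP treatment used after the Day 1 visit.
- **SAP 6.2, Table 12** derives the time in years since the last EFP treatment as "Date of most recent EFP treatment – Date of informed consent/365.25" and points to 6.3.1.3 for incomplete dates.

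**The concern.** The exception in 6.3.1.3 has an evident purpose: it stops an imputed end date from landing after dosing. But its only test is the year. It does not ask whether the month is missing, or whether the known month already lies before the injection. As written, it replaces the whole date, so information that the subject gave and the site recorded is thrown away.

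What is at stake is the accuracy of the treatment-history outputs. SAP 7.5 tabulates prior and concomitant medications, procedures and EFP treatments by region, and SAP 6.1 lists all derived variables. In an open-label study with no control group, a reader will look at those tables to see whether other cellulite therapy overlapped with the study. A treatment that ended months earlier should not appear to run up to Day 1, and an elapsed time should not be negative.

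**Working it through.** The plan gives no figure to reproduce. The check applies the date rules to partial records.

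**Inputs.** First injection 26 December 2019 (the first dosing date in Protocol 2.1). A second injection date, 15 September 2020, is assumed for illustration. Consent and Screening are assumed to fall 35 days before injection, the maximum in Protocol 5.4: 21 November 2019 and 11 August 2020.

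**Rules.**
- Literal 6.3.1.3: end year = injection year gives the injection date.
- Month-end (SAP 6.3.1, and also 6.3.1.3 if its exception applies only to a missing month): last day of the known month.
- Table 12, with the intended brackets: (treatment date - consent date)/365.25.

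| Injection | Recorded end | Literal 6.3.1.3 | Month-end | Shift (days) | Table 12, literal | Table 12, month-end |
|---|---|---|---|---|---|---|
| 26 Dec 2019 | Jan 2019 | 26 Dec 2019 | 31 Jan 2019 | 329 | +0.096 y | -0.805 y |
| 26 Dec 2019 | Mar 2019 | 26 Dec 2019 | 31 Mar 2019 | 270 | +0.096 y | -0.643 y |
| 26 Dec 2019 | Jun 2019 | 26 Dec 2019 | 30 Jun 2019 | 179 | +0.096 y | -0.394 y |
| 15 Sep 2020 | Jan 2020 | 15 Sep 2020 | 31 Jan 2020 | 228 | +0.096 y | -0.528 y |
| 15 Sep 2020 | Jun 2020 | 15 Sep 2020 | 30 Jun 2020 | 77 | +0.096 y | -0.115 y |

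For the March 2019 record: 30+31+30+31+31+30+31+30+26 = 270 days from 31 March to 26 December. Consent lies 270 - 35 = 235 days after 31 March, and 235/365.25 = 0.643. The literal rule gives 35/365.25 = 0.096 with the opposite sign.

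**Concomitant status.** In each row the literal date is after Screening and the month-end date is before it. With a complete start date, the treatment is therefore concomitant under SAP 4.3 on the literal rule and not concomitant on the month-end rule.

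**Where the exception does useful work.** With injection on 15 September 2020, an end date of 2020 alone would otherwise become 31 December 2020, 107 days after Day 1. September 2020 would become 30 September, 15 days after.

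**The narrower reading.** If the exception covers only a missing month, known earlier months survive. But the September 2020 record then goes to 30 September, after Day 1, which looks like the post-Day-1 use that SAP 4.4 reports as a violation. Neither reading gives a sensible date in every case.

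**Table 12.** Without brackets, only the consent date is divided by 365.25. With them, any treatment that ended before consent gives a negative value. The March 2019 record should give (21 Nov 2019 - 31 Mar 2019)/365.25 = +0.643 years.

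**The case against.** The strongest reply is that the sentence is ambiguous. The exception follows the December clause directly and can be read as belonging to it alone. SAP 6.3.1.3 is also the specific rule and 6.3.1 the general one, so a difference between them need not be an error. Both points are fair. They reduce the finding to a literal reading, but the SAP does not say which reading is meant, two programmers could code it differently, and the narrower reading has its own fault.

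A reader might go further and infer that the rule turns finished treatments into banned use on Day 1, creates eligibility breaches and leads to subjects being discounted. The documents do not support that chain:

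- Prior EFP status depends on the start date, so the record stays prior.
- The SAP 4.4 violation needs use after the Day 1 visit, and the literal rule never gives a same-year end date later than Day 1.
- SAP 6.3.1.1 keeps a medication with a partial onset before consent out of the concomitant class.
- SAP 4.2 draws deviations from eCRF data, vendor data and monitoring reports, and does not mention imputed dates. Eligibility is verified before dosing.
- The Evaluable Population depends on PR-PCSS data and, in the protocol, on the date of first dose. No per-protocol population is defined.

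The scope is also narrow. Liposuction, injections, radiofrequency, laser, cryolipolysis, surgery and investigational treatments carry 12-month washouts, so an eligible subject cannot have had them earlier in the injection year. Massage (3 months), Endermologie-type treatment (6 months) and creams or home therapies (2 weeks) remain.

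On Table 12, the derived time is not among the baseline summaries in SAP 7.3, and SAP 7.4 says that EFP history is not summarized. It would still be listed under SAP 6.1. Nor is a positive value proof of a wrong imputation: a treatment that ended between consent and Day 1 is positive too.

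**Conclusion.** The concern holds in a limited form. Read literally, SAP 6.3.1.3 replaces a known earlier month by the first injection date whenever the years match, in conflict with SAP 6.3.1. In the cases worked here the shift runs from 77 to 329 days. It can make a finished massage course, Endermologie-type treatment or cream with a complete start date appear as concomitant in the SAP 7.5 tables, and it distorts the time since last EFP treatment. Independently of how the exception is read, the Table 12 formula lacks brackets and has the wrong sign for true past treatments.

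No efficacy endpoint or analysis population is affected. False deviations are a possibility if someone uses the imputed dates for that purpose; they are not a stated result of the plan. The size shown rests on the literal reading, one dosing date from the protocol, one assumed dosing date, and an assumed 35-day interval from consent to injection. The documents do not show how many subjects would have such records.

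**What to change.** Rewrite the end-date rule in SAP 6.3.1.3 as follows:

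1. If the month is known, impute the last day of that month. If only the year is known, impute 31 December.
2. In either case, if the result is later than the first injection date and the treatment is not recorded as ongoing or as used after Day 1, set it to the first injection date.

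The cap must stay. Deleting the exception outright would put a 2020-only record at 31 December 2020, 107 days after a 15 September injection. The condition on later use must stay too, so that a known month after the injection month is not pulled back to Day 1. With this rule, March 2019 gives 31 March 2019, while December 2019 and 2019 alone give 26 December 2019 for the first subject's dosing date.

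Change Table 12 to (date of informed consent - date of most recent EFP treatment)/365.25. State in SAP 4.2 or 6.3.1.3 that an imputed date alone does not create a protocol deviation, and say that 6.3.1.3 takes precedence over 6.3.1 for EFP treatments.

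The cost is a few sentences and a small programming change, with no new data. SAP section 8 bases the plan on the original protocol and Amendment 1, while the protocol is now at Amendment 3, so the SAP needs a revision in any case.

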6.4. Interim Analyses

An interim analysis will be conducted when all subjects have completed their Day 71 visit. Analysis of all primary and secondary endpoints will be included in the interim analysis.

The purpose of the interim analysis is to determine if changes in morphology and/or histology can be identified using MRI and biopsy. If the interim analysis does not indicate that such changes can be identified, subsequent or additional MRIs or biopsies will not be done in this study.

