9.3.2. MRI and Biopsy Analyses

A descriptive summary of changes from baseline seen in MRI and biopsy results will be provided for the Evaluable Population.

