9.4. Interim Analysis

An interim analysis will be conducted when at least 4 of the 12 subjects who received their first dose of study drug after 18 March 2020 have completed their Day 71 visit. For all subjects who received their first dose of study drug after 18 March 2020, analysis of all primary, secondary,

and tertiary endpoints will be included in the interim analysis. For the subjects who received all three doses prior to 18 March 2020, their MRI and biopsy data, if available, will be assessed separately but included in interim analysis. The purpose of the interim analysis is to determine if changes in morphology and/or histology can be identified using MRI and biopsy. If the interim analysis does not indicate that such changes can be identified, subsequent or additional MRIs or biopsies will not be performed in this study.

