3. STUDY DESIGN AND MEASURES

3.1. Study Design

This is a single center, open-label, Phase 2a study to assess the safety and efficacy of CCH in adult women with moderate or severe edematous fibrosclerotic panniculopathy (EFP) of the buttocks or thighs using photonumeric scales, MRI, and histopathology of tissues from the treated area. Approximately 18 subjects will be screened in order to dose approximately 12 subjects. Every attempt will be made to enroll an equal number of subjects across the 2 severity levels in both buttocks and thighs (eg, 3 subjects with moderate buttock cellulite, 3 subjects with severe buttock cellulite, 3 subjects with moderate thigh cellulite, and 3 subjects with severe thigh cellulite).

Following a screening period of approximately 35 days, qualified subjects will receive 0.84 mg of CCH per treatment area (buttock or thigh) for a total dose of 1.68 mg in both buttocks or both thighs per treatment session for 3 sessions. Treatment sessions will occur approximately 21 days apart (Day 1, Day 22, and Day 43). Following treatment and assessments at Day 71, subjects will be assessed and followed for an additional 194 days.

Statistical Analysis Plan (SAP) Module 1 – Protocol EN3835-212

Subjects will have MRIs and double punch biopsies of 3 selected target dimples 3 times during the study (Screening, Day 71, and Day 251).

Subjects will participate in the study for up to approximately 305 days (approximately 10 months). The duration of the study from first subject first visit to last subject last visit will be dependent upon the ability of the site to identify and enroll subjects. The entire study is expected to require approximately 12 months to complete.

Table 2 below describes the schedule of activities and assessments performed during screening, the treatment phase, and the extension phase of the study.

Table 2: Schedule of Activities

Activities	Screening (Day -35 to Day -1)			Treatment Phase				Extension Phase			
	Before MRI	Before biopsy	Approximately Day -14	Day 1 Treatment Session I	Day 22 (± 3 Days) Treatment Session II	Day 43 (± 3 Days) Treatment Session III	Day 71 (+10 Days)	Day 85 (±5 Days)/ Biopsy Follow-up	Day 161 (± 15 Days)	Day 251 (±15 Days)/ Early Termination	Day 265 (±5 Days)/ Biopsy Follow-up
Informed consent ^a	X										
Inclusion/exclusion criteria review ^b	X			X							
Medical and surgical history	X										
EFP history	X										

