5. ANALYSIS POPULATIONS

The study will use the following analysis populations for data summarization.

Table 11: Analysis Population

Population	Definition	Displays
Safety Population	The Safety Population will include all subjects who have undergone any MRI or biopsy at Screening.	All demographic and baseline characteristics as well as safety parameters will be summarized based on this population.
Evaluable Population	The Evaluable Population will include all subjects in the Safety Population who have a baseline and at least 1 post-injection PR-PCSS evaluation.	All efficacy analyses will be based on this population.

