7.8. Pharmacodynamics

Pharmacodynamic parameters, if available, will be summarized by treatment region (buttock or thigh) using the Safety Population.

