8. CHANGE FROM PROTOCOL

This SAP is prepared primarily based on the study protocol; original version dated October 22, 2019 and protocol amendment 1 dated January 16, 2020.

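### SAP 6.4 delays the MRI/biopsy stop-or-continue interim until all subjects complete Day 71, while protocol 9.4 allows it from 4 of 12; the MRI/biopsy analysis populations also differ

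*SAP*

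**What the plan says.** **Interim.** SAP 6.4: "An interim analysis will be conducted when all subjects have completed their Day 71 visit". Protocol 9.4 sets the trigger at Day 71 completion by "at least 4 of the 12 subjects who received their first dose of study drug after 18 March 2020". For subjects who had all three doses before that date, protocol 9.4 adds that "their MRI and biopsy data, if available, will be assessed separately but included in interim analysis"; SAP 6.4 has no such provision. SAP 6.4 covers primary and secondary endpoints, and protocol 9.4 covers tertiary endpoints as well. Both give the same purpose and consequence: if MRI and biopsy show no identifiable change, no more of either will be done.

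**Basis of the SAP.** SAP section 8: "This SAP is prepared primarily based on the study protocol; original version dated October 22, 2019 and protocol amendment 1 dated January 16, 2020". SAP section 9 calls it the first version. SAP 3.1 still plans the earlier study: "Approximately 18 subjects will be screened in order to dose approximately 12 subjects". Protocol 4.1 now plans about 19 dosed subjects, 12 of them new.

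**Population for MRI and biopsy.** SAP 7.8: "Pharmacodynamic parameters, if available, will be summarized by treatment region (buttock or thigh) using the Safety Population"; sections 7.8.1 and 7.8.2 repeat that population. Protocol 9.3.2: "A descriptive summary of changes from baseline seen in MRI and biopsy results will be provided for the Evaluable Population". SAP Table 11 defines the latter set thus: "The Evaluable Population will include all subjects in the Safety Population who have a baseline and at least 1 post-injection PR-PCSS evaluation". Protocol 9.2 also requires the first dose to fall after 18 March 2020. The Safety definitions differ too: any screening MRI or biopsy in the SAP, the screening biopsy in the protocol.

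**The concern.** This interim is the only study-wide rule in the documents for halting further MRIs and 8 mm double punch biopsies. Protocol 9.1 justifies 12 subjects partly by keeping the number exposed to an invasive procedure as small as possible. An interim held only after every subject's Day 71 visit comes after every Day 71 biopsy, so it cannot serve that aim at Day 71. Protocol 9.3 requires a final SAP before the interim, so the SAP is where an analyst would look for the trigger, the endpoints and the analysis set.

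The population question is separate and smaller. Protocol 4.1 bases efficacy on the 12 new subjects. Without the date cut-off, the SAP would mix pre-suspension subjects into the MRI/biopsy summaries and, because SAP 7.6 uses its Evaluable Population, into the efficacy analyses as well.

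**Working it through.** **Inputs.** Twelve new subjects, about 19 in total (protocol 4.1). Seven dosed before the suspension, of whom 2 had three doses and 1 had two (protocol 2.1). One biopsy per subject at Day 71 and one at Day 251 (SAP 3.14.2). Cohort check: 7 + 12 = 19, as the protocol states. Post-treatment biopsies in the new cohort: 12 + 12 = 24.

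**Set-up.** Let subject i (1 to 12) receive the first dose p days after the previous subject, with visits on nominal days, and let t be the days from trigger to decision. The documents give neither p nor t. The protocol decision falls at 3p + 71 + t (cut at exactly 4 completers) and the SAP decision at 11p + 71 + t.

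**Day 71 biopsies still avoidable.**
- Protocol: (i − 1)p + 71 > 3p + 71 + t, that is, i − 4 > t/p. At t = 0 this leaves subjects 5 to 12: 12 − 4 = 8. None is left once t ≥ 8p.
- SAP: (i − 1)p + 71 > 11p + 71 + t, which no i up to 12 satisfies: 12 − 12 = 0 at any pace. Reading all subjects as the 19 rather than the 12 does not change this.

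**Day 251 biopsies still avoidable.**
- Protocol: all 12 if 3p + t < 180. In the slowest case below, 3 × 24.6 + 60 = 133.8.
- SAP: (12 − i)p < 180 − t. All 12 remain avoidable if 11p + t < 180.

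**Illustration** (assumed paces; t = 0/30/60 days):

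| p (days) | Day 71, protocol | Day 71, SAP | Day 251, protocol | Day 251, SAP |
|---|---|---|---|---|
| 6.7 | 8/4/0 | 0 | 12 | 12/12/12 |
| 9.8 | 8/5/2 | 0 | 12 | 12/12/12 |
| 13.2 | 8/6/4 | 0 | 12 | 12/12/10 |
| 24.6 | 8/7/6 | 0 | 12 | 8/7/5 |

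Example: p = 13.2 and t = 30 give t/p = 2.27, so subjects 7 to 12 qualify, which is 6. At p = 6.7 a 60-day turnaround exceeds 8 × 6.7 = 53.6 days and the two triggers give the same result. At p = 24.6 the gain lasts until 8 × 24.6 = 196.8 days. The SAP trigger begins to lose Day 251 biopsies at p = 180/11 = 16.4, 150/11 = 13.6 or 120/11 = 10.9 days for t = 0, 30 or 60.

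**Why the paces are assumptions.** Pre-suspension first-dose dates cannot be worked back from visit windows. The first subject was dosed on 26 December 2019, so nominal Day 71 was 5 March 2020 and its +10-day window closed on 15 March, before the suspension on 18 March. Yet protocol 2.1 says that no subject had completed all Day 71 assessments. Subjects therefore cannot be presumed in window at the suspension, and the new cohort's pace is unknown in any case.

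**Population.** Subjects with fewer than three doses before the suspension have no Day 71 or Day 251 biopsy (protocol 8.6.2). Biopsy change can therefore gain at most the 2 full-course subjects: 12 + 2 = 14. Those with fewer than three doses keep their MRIs if willing (protocol 4.1), so MRI change can gain up to 7: 12 + 7 = 19. Of these, 7 − 2 = 5 had fewer than three doses before the suspension. Replacing Safety by Evaluable in SAP 7.8 would not align the documents, because the SAP Evaluable set has no date cut-off and is nested in a Safety set that is itself defined differently.

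**The case against.** The strongest reply is version lag. The SAP says what it was built on, and the protocol's amendment summary shows that the all-subjects trigger was the rule until Amendment 2. Biopsies are scheduled by the protocol, protocol section 8 makes adherence to it mandatory, and the SAP refers to the protocol for study details. On this view nobody would hold the interim late because of an old SAP, and a later version may exist. This explains the cause and stands as a limit: the SAP's date relative to Amendments 2 and 3 is not given. It does not remove the conflict, because the SAP supplied is the only one in the documents and records no departure on trigger or population.

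Four stronger readings are tempting and are not supported:
- *The two triggers cannot both be met.* The protocol sets a floor with no upper limit or deadline, so an interim at 12 of 12 would meet its literal wording. The natural reading is an early look, and the SAP excludes one.
- *Eight biopsies would be lost.* Eight is a ceiling, and it matters only after a negative interim.
- *The SAP interim serves no purpose.* It can still stop Day 251 MRIs and biopsies, in some cases for all 12 subjects.
- *Biopsy results would be diluted by partly treated subjects.* Only 2 subjects could be added, both with all three doses, and the protocol itself brings their data into the interim, shown separately.

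The missing tertiary endpoints matter little: they are Day 161 and Day 251 measures and would be largely empty at the protocol trigger.

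**Conclusion.** Wrong as written: a protocol–SAP inconsistency. On the current texts, a negative interim can avoid 0 of 12 Day 71 biopsies under the SAP trigger and up to 8 of 12 under the protocol trigger. The zero holds at any pace. The 8 requires a cut at exactly 4 completers and an immediate decision; with an assumed 30-day turnaround it becomes 4 to 7 over the illustrated paces, and with 60 days 0 to 6. These counts assume even accrual, nominal visit days and no dropout, and they leave out any biopsies in the 2 pre-suspension full-course subjects.

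The population conflict is real but secondary: at most 2 extra subjects for biopsy change and up to 7 for MRI change. The missing cut-off carries over to the efficacy analyses. The documents show no cause for the choice of the Safety Population in SAP 7.8. The table layouts in SAP Module 2 were not available.

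**What to change.** Make one SAP revision before the interim, as protocol 9.3 already requires the SAP to be final by then:

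- (a) Reconcile SAP 6.4 with protocol 9.4 on the trigger, the endpoint set and the separate display of subjects who had all three doses before 18 March 2020. Note that tertiary endpoints will be largely empty at that point.
- (b) Reconcile both the Safety and the Evaluable definitions in SAP Table 11 with protocol 9.2, including the 18 March 2020 first-dose cut-off.
- (c) Use that Evaluable Population in SAP 7.8, 7.8.1 and 7.8.2, with the pre-suspension full-course subjects shown separately.
- (d) Bring SAP sections 3.1, 3.3 and 8 up to Amendment 3.

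The cost is the revision and an earlier data cut that the protocol already plans. No new data are collected.
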